3.1.1 Study Schema

We will enroll 20 adult subjects with Syn-ILD across 5 clinical sites. We expect enrollment to be completed within 15 months. A 1:1 randomization scheme for active drug: placebo as a weekly SQ injection with their SOC for 24 weeks. All patients can then enter an optional open label follow-up after the 24-week randomized, controlled phase, during which all subjects receive 24 weeks of ABT in the same fashion as the initial study phase. This follow-up phase will assess durability, long term response and safety in patients who were in the active treatment arm while allowing the placebo arm to receive active drug, thus improving recruitment and study power.

Patient must have active ILD associated with anti-synthetase syndromes (a subset of myositis) that are being given SOC treatment for ILD. Patients could have refractory disease with flare up or new onset disease. Patient may or may not have active myositis (PM/DM). We anticipate the continued participation of all subjects in open label extension phase.

Open label phase: At the end of the active study period (week 24 closing visit), patients in either arm can enroll into the optional open-label phase of 24-week ABT therapy (125 mg SQ injection weekly).

a. **Standard of Care (SOC):** The SOC of patients with Syn-ILD includes steroids OR another IS agent OR a combination of steroid and another IS agent. Thus, we will allow steroids and/or only 1 additional IS agent. **Additional IS agent can be either mycophenolate mofetil (MMF) or azathioprine (AZA), but not both.** Patients on steroids alone can be enrolled without additional IS agent. Maximum dose allowed for MMF is 3 gms/day and for AZA is 200 mg/day. Patient should be on stable dose of MMF or AZA for 4 weeks and/or stable dose of steroids 2 weeks prior to Visit 1. Visit 1 is the time of first ABT/placebo dosing. Overall goal is to enroll patients into the trial as soon as the SOC drug has achieved stable dosing. Prednisone taper will be allowed at maximum dose of 60 mg at baseline (Visit 1), at which time a forced prednisone taper will commence as outlined below. Dose of concomitant medication cannot change throughout the phase I of the trial (24 weeks) unless safety/toxicity issues supervene.

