No other concomitant IS agent is allowed (e.g. IVIG, plasmapharesis, rituximab, methotrexate, tacrolimus, cyclosporine, other biologics. Hydroxychloroquine and pirenade **are permitted** during the trial if on a stable dose for 4 weeks prior to trial entry.

Forced steroid taper (Prednisone or other steroid in prednisone equivalent doses) in subject on a stable dose of steroid 2 weeks prior to visit 1.

a. **Steroid Tapering:** May begin within or at 1 week after beginning study drug. Goal is to taper steroid to 5 mg or lower dose within 8 weeks. Recommended daily prednisone taper (or other forms of steroid in equivalent doses)

- i. 60 mg decreased to 40 mg after 1 week
- ii. 40 mg decreased to 30 mg after 1 week
- iii. 30 mg decreased to 20 mg after 1 week
- iv. 20 mg decreased to 15 mg after 1 week
- v. 15 mg decreased to 10 mg after 1 week
- vi. 10 mg decreased to 7.5 mg after 1 week
- vii. 7.5 mg decreased to 5 mg after 1 week
- viii. Further decrease as per treating physician.

b. **Steroid at Entry:** Maximum steroid dose allowed at study entry is ≤ 60 mg/day prednisone (or other forms of steroid in equivalent doses). If on a lower dose then the tapering scheme noted above should be employed based on the entry dose. Patients not on steroids are allowed in the study and are not allowed to start new steroids unless there is a disease flare.

c. **Steroid Dosing During Flare:** If in the clinical site investigator's opinion there are complications or worsening of disease that necessitate an increase in the prednisone dose (or other forms of steroid in equivalent doses) then the smallest reasonable increase should be considered (maximum increase of prednisone equivalent of 20 mg/day is allowed). After the increase, subjects should resume the prednisone taper noted above.

Concomitant medications will remain unchanged throughout Phase I, except changes made per the rescue medication protocol. During the open label Phase II, concomitant medications adjustments are permitted even if the subject has not met the definition of worsening.

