4.5.3 Rescue Medications

If in the clinical site investigator’s opinion there are complications or worsening of disease (meeting worsening criteria) that necessitate an increase in concomitant immunosuppressive therapy the following guidelines should be followed:

- The steroid dose may be increased by ≤ 20 mg (prednisone equivalent) daily. After 2 weeks of increase the forced corticosteroid taper will commence as noted above. Such patients will remain on the trial protocol (on study drug), and it will not be considered as treatment failure.
- Requirement of additional non-steroid IS therapy or requirement of increase of steroids dose > 20 mg equivalent of prednisone for worsening ILD as rescue therapy (after initial 8 weeks of study drug) will be considered a treatment failure. Such patients can be continued on the trial protocol (on study drug) only if rescue drug include either one of them: MMF, AZA, tacrolimus, cyclosporine, IVIG, methotrexate AND maximum of one non-steroid IS

therapy is given during the trial. Steroids can be concomitantly increased with non-IS agent.

- Note if additional non-steroid IS therapy or increase of steroid dose > 20 mg equivalent of prednisone occurs <8 weeks on study drug, then these patients are not considered treatment failure as not enough time to have outcome assessment.
- Biological drugs, cyclophosphamide, plasmapheresis, are not allowed as rescue therapy and will lead to withdrawal from the trial drug/placebo protocol (i.e stopping trial drug/placebo) for safety reasons. Similarly, more than one non-steroid IS agent is not allowed as rescue therapy and will lead to withdrawal from the trial drug/placebo protocol (i.e. stopping trial drug/placebo). But all patients despite withdrawal from trial drug/placebo will be followed for at least 24 weeks for clinical evaluation. Note withdrawal from trial drug/placebo as above is not considered with withdrawal from the study.

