For example: If a patient is having severe worsening at 3 months while on AZA and the study drug; investigator/treating physician can give rescue steroid increase by 20 mg prednisone (or new prednisone 20 mg if patient was not on steroid) without any changes in the outcome or trial protocol. However, if for some reason the investigator/treating physician needs to start MMF on the patient, then the patient can continue on the trial protocol (on study drug) as long as AZA is stopped (so only one non-steroid immunosuppressive drug is given concomitantly with study drug). Concomitant increase of steroid is OK. Such scenarios should be avoided as these patients will be considered as treatment failure.

Specifically related to this trial, there are several scenarios for subjects as they are followed through the 6 month trial:

1. Subjects can withdraw from the study drug (active drug/placebo) at any time for various reasons deemed appropriate by PI. They are then treated at the discretion of the PI off the study drug, but should continue to be followed at the regular study time points for the duration of the trial for efficacy and safety data monitoring. No randomization scheme will be broken/revealed. Withdrawal from study drug doesn't mean withdrawal from the study.
2. If the criteria for the worsening are formally met but the subject and PI do not feel it is necessary to change therapies other than allowed rescue therapies (as above), then the subject will remain on the trial protocol (study drug). No randomization scheme will be broken/revealed.
3. If criteria for the worsening is formally met and the subject and/or the PI feel that "escape" therapy other than allowable rescue agents is necessary, then the subject will be treated at the discretion of the PI off the trial protocol (withdrawal from study drug), but should continue to be followed at the regular study time points for the duration of the trial for efficacy and safety data monitoring. No randomization scheme will be broken/revealed. Withdrawal from study drug doesn't mean withdrawal from the study.

Refer to Appendix C for rescue medication diagram.

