12.0 STATISTICAL CONSIDERATIONS

12.1 Determination of Sample Size

The sample size is 20 patients with 10 patients in each arm for a 24-week randomized double blind clinical trial. The sample size is justified based on this trial being a proof of concept pilot study. This study will allow us to determine an initial signal for possible efficacy of ABT in Myositis-ILD (Syn-ILD) as well as give safety and tolerability data. Moreover, it will allow us to determine an estimate of the effect size of the study drug and placebo to design a more definitive phase II/III clinical trial. In our cohort about 25% patients with SOC decline by FVC% of $\geq 15\%$ or death or

transplant. Assuming FVC decline by mean of 10% on SOC therapy and trial drug + SOC leads to improvement in FVC% (Even by mean of 5%) we will have >90% power to detect the difference with sample size proposed. Based on our database there is about 25% patients that decline FVC > 10% on SOC for myositis ILD.

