12.3 Methods of Analysis

Primary End Point:

The primary end point for statistical analysis will be the percent FVC changes from baseline to week 24 between the 2 treatments arms (SOC/placebo vs. SOC/ABT). Ranked ANCOVA, with average standardized rank change in the predicted FVC% as the outcome measure and the standardized rank baseline as a covariate will be used. Primary outcome criteria for safety and

tolerability will be adverse event (routine adverse events or tolerability issues and serious adverse event) between the 2 treatment arms (SOC/placebo vs. SOC/ABT). Chi-square (or Fischer exact test) and t-test (or Mann-Whitney) will be used based on data variable and distribution. Patients will be stratified for sub-analysis based on their SOC drug

Secondary Analysis (SOC/placebo vs. SOC/ABT) for Syn-ILD:

- a. Time to progression free survival where progression is defined as first occurrence of any of the following: death or lung transplant or $FVC \geq 10\%$ decline *or* $FVC \geq 5\%$ decline with $DLCO \geq 15\%$ decline. This will be done using Cox proportional hazards model and controlling for baseline demographics and $FCV\%$.
- b. Change in dyspnea, as measured by University of California San Diego Shortness of Breath Questionnaire (UCSD SOBQ) (range 0-120, higher score is worsening dyspnea), will be done using Mann-Whitney test.
- c. Time to improvement in $FVC\%$ by $\geq 10\%$. This will be done using Kaplan Meier survival curve and Cox's proportional hazards model after controlling for co-variates.
- d. Rates of death or requiring lung transplant using Chi-square (Fischer exact) test.
- e. Other individual PFT variables (FEV1%, DLCO%) similar to analysis done for primary outcome of $FVC\%$.
- f. Qualitative changes in HRCT chest over 6 months in the two arms using chi-square (or Fischer exact) test. Changes in semi-qualitative scoring of fibrosis over 6 months based on HRCT chest scan images collected from all sites and centrally read by an expert blinded radiologist, will be done as a separately and analyzed using analysis strategy similar to primary outcome.
- g. Steroid-sparing effect (calculated using prednisone dose equivalents) using paired t-test.
- h. Frequency of treatment failures: a) patient meeting worsening criteria or withdrawal due to worsening ILD anytime during the trial or b) $FVC\%$ worsening by 10% at 6 months, c) death or transplant within 6 months. Chi-square test will be used to compare between the two groups.

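### Section 12.3 item g assigns the steroid-sparing effect a paired t-test, which cannot compare the two unmatched arms named in its own heading

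*Combined protocol and SAP*

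**What the plan says.** Section 12.3 groups items a to h under the heading "Secondary Analysis (SOC/placebo vs. SOC/ABT) for Syn-ILD", which sets the contrast as placebo against abatacept. Item g reads "Steroid-sparing effect (calculated using prednisone dose equivalents) using paired t-test". Section 3.3.2 item g and Section 12.2.2 item g list the same endpoint without a test. All three places give the unit (prednisone equivalents), but none gives a summary measure, a time point or a between-arm method. Section 2.2 names the sparing of steroids by abatacept as a secondary objective.

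The design is parallel: "A 1:1 randomization scheme for active drug: placebo as a weekly SQ injection" (Section 3.1.1) and "The sample size is 20 patients with 10 patients in each arm" (Section 12.1). No matching is described. The sub-analysis by background drug in Section 12.3 is stratification, not pairing.

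Section 3.1.1 sets a steroid taper without distinguishing the arms: "Goal is to taper steroid to 5 mg or lower dose within 8 weeks". It also admits patients who take no steroids. For an allowed rescue increase of up to 20 mg/day, Section 4.5.3 says "After 2 weeks of increase the forced corticosteroid taper will commence as noted above".

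**The concern.** A paired t-test needs a natural partner for each observation. In two independently randomized arms, the only natural partner is the same patient at another time. Item g therefore names a test that does not carry out the comparison in its heading.

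What is at stake is the meaning of the result. The protocol itself pushes steroid dose down in both arms. A test of change over time would largely reflect that taper. It could not show whether dose fell further with abatacept than with placebo, and the objective concerns that difference. If the conflict is left until unblinding, someone must then choose a different test with the data in view.

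**Working it through.** The plan gives no sample size, effect or alpha for item g, so there is no figure of its own to reproduce. The >90% power in Section 12.1 concerns FVC% and does not bear on this point.

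**1. Item g beside its neighbours.** In Section 12.3, items a and c use Cox models, b uses Mann-Whitney, d and h use chi-square (d with a Fisher option), e follows the primary analysis, and f uses chi-square/Fisher and the primary analysis. None is a paired test. Item g is the only exception.

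**2. Reading A: pairs across arms.** The statistic is t = d̄ / (s_d/√n) with n = 10 pairs and 9 df. The mean difference d̄ is the same for every matching. The SD of the differences, s_d, changes with the matching, and so does p. In one simulated 10 + 10 data set, the independent test gave p = 0.18, while random re-pairings of the same data gave p from 0.009 to 0.34. Degrees of freedom fall from 18 to 9 and the critical t rises from 2.101 to 2.262. At a standardized difference of 1.0 (noncentrality 1.0 × √(10/2) = 2.236), power falls from 56% to 51%.

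**3. Reading B: each patient's own doses over time.** Within an arm, mean change = change due to the taper + any drug effect. The paired test asks whether this sum is 0. Only the difference between arms removes the taper term.

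A hand example, with all doses assumed:
- In each arm, one patient enters at each step of the Section 3.1.1 taper (60, 40, 30, 20, 15, 10, 7.5, 5 mg) and two take no steroids.
- Everyone above 5 mg reaches 5 mg, and abatacept does nothing.
- Changes: -55, -35, -25, -15, -10, -5, -2.5, 0, 0, 0. The sum is -147.5 and the mean is -14.75 mg/day.
- Sum of squares 5231.25 - 147.5²/10 = 3055.625. SD = √(3055.625/9) = 18.43. SE = 18.43/√10 = 5.83.
- t = -14.75/5.83 = -2.53, df 9, p = 0.032, 95% CI -27.9 to -1.6, the same in both arms.
- Between-arm difference: -14.75 - (-14.75) = 0.

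A simulation under no drug effect (40,000 trials, 10 per arm, two-sided 5%) used assumed mean falls of 5 to 20 mg/day and SDs of 10 to 15. The paired test was significant in the abatacept arm in 29% to 99% of trials. It was significant in the abatacept arm but not the placebo arm in 1% to 21%. An independent two-sample test on change rejected in 4.9% to 5.2%.

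**4. Which estimate belongs beside a ranked ANCOVA?** An assumed scenario was simulated: 75% of patients on steroids, entry doses 5 to 60 mg, and 50% of placebo against 0% of abatacept patients 20 mg higher at week 24. The ranked ANCOVA on change rejected in about 62% to 66% of trials. The unadjusted Hodges-Lehmann interval covered 0 despite a significant test in about 51% to 56% of all trials, which is roughly four in five of the significant ones. That interval inverts the Mann-Whitney test on change, which ignores entry dose and rejected in only 15% to 20% of trials in this scenario. The test and the estimate should therefore be adjusted in the same way.

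**The case against.** The strongest reply is that the heading already prescribes the between-arm contrast, so *paired* may simply be a slip for *unpaired*. That is possible, and the documents do not settle it. If so, the repair to the test is one word, but the text as it stands still names a test that cannot be applied to the stated contrast.

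A second reply is that a within-patient test is legitimate as a description of each arm. It is, but it leaves the heading's comparison and the Section 2.2 objective without a test.

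A third reply is that the taper does not guarantee a fall. Section 3.1.1 calls the steps recommended, lets the taper start up to a week after study drug, leaves reductions below 5 mg to the physician, and admits patients on no steroids. This stands against any numerical claim. It does not alter the fact that a decline is expected in both arms, because the same goal applies to both.

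A reader might infer that the trial will report a taper-driven fall as steroid sparing, or that item g carries a false-positive rate of 29% to 99%. The documents support neither. The first presumes Reading B and a conclusion the plan never states. The second rests on assumed doses and SDs.

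The weight is also fairly questioned: this is one of ten ILD secondary outcomes (a to j) in Section 3.3.2.

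**Conclusion.** The point holds. The named test does not fit the named comparison under either reading, and no other section supplies a test that does. This conclusion follows from the text and needs no numerical assumption.

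Its practical size cannot be determined, because the documents give no entry-dose mix, share of patients on steroids or flare rate. The p = 0.032 example and the simulated rates show the mechanism only.

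The consequence is confined to one secondary endpoint of a 20-patient proof-of-concept study. The primary FVC% analysis, the sample size and the safety comparison are unaffected. It should be corrected before unblinding, but it does not threaten the trial.

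**What to change.** In Section 12.3 item g, replace the paired t-test with an independent-groups comparison. For example: *Change in prednisone-equivalent daily dose from Visit 1 to week 24, counting steroid-free patients as 0 mg and including rescue steroid, will be compared between arms by the ranked ANCOVA used for the primary endpoint, with Visit 1 dose as covariate.* This matches the primary model, which takes "average standardized rank change in the predicted FVC% as the outcome measure".

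Report a between-arm estimate with a 95% CI that is also adjusted for Visit 1 dose, for example from an ANCOVA on week-24 dose with a bootstrap or permutation interval. Do not pair the test with an unadjusted Hodges-Lehmann interval. Label any paired within-arm result as descriptive. State how a patient with no week-24 dose is handled.

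If dated dose changes are captured, also compare cumulative prednisone-equivalent dose over weeks 0 to 24 between arms. A week-24 dose misses earlier increases that have since returned to the taper under Section 4.5.3.

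The cost is a few sentences in Section 12.3, with no change to dosing, taper or visits. Section 7.2 already reviews concomitant medications at weeks 0, 12 and 24, and patients who stop study drug "should continue to be followed at the regular study time points for the duration of the trial". The cumulative measure needs dated dose changes, which Section 7.2 and Appendix B do not clearly say are recorded.

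The downside is low power. With the assumed entry doses of step 4, the ranked ANCOVA has about 17% to 19% power if 25% of placebo and 0% of abatacept patients are 20 mg higher at week 24, and about 62% to 66% at 50% against 0%. The estimate and interval will be more useful than the p-value.

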APPENDIX A: MMT-8

MMT- 8 is a set of 8 designated muscles tested unilaterally (potential score 0-70 and usually

tested on the right side unless contraindicated) or bilaterally (potential score 0-140) and if axial (neck flexor) testing is included, potential score = 150. The scale of 150 is proposed for this trial.

Muscle Groups	Right (0 – 10)	Left (0 – 10)
Axial Muscles (0 – 10)		
Neck Flexors	0-10	
Proximal Muscles (0 – 50)		
Deltoid	0-10	0-10
Biceps brachii	0-10	0-10
Gluteus maximus	0-10	0-10
Gluteus medius	0-10	0-10
Quadriceps	0-10	0-10
Distal Muscles (0 – 20)		
Wrist extensors	0-10	0-10
Ankle dorsiflexors	0-10	0-10
MMT- 8 score (0 – 150)	0-70	0-80

APPENDIX B: STUDY FLOW CHART/SCHEMA

Month	0-21 days before study drug	Open Label												Unscheduled Visit
		0	1	2	3	4	5	6	7	8	9	10	11	12
(weeks)	0	+7 days from V1	8	12	16	20	24	28	32	36	40	44	48	
Visit	Screen	1	Call	Call	2	Call	Call	3	Call	Call	4	Call	Call	5
	or													
	Visit 0													
Safety Laboratory Testing														
Urine Pregnancy (if applicable)	X	X			X			X			X			X
CK, Aldolase		X			X			X			X			X
CBC, Creatinine, LFT		X			X			X			X			X
Serologies (HCV, HBV) or TB screening if not done within last 1 year	X													
Data Collection														
Screening demographics	X													
Screening evaluation	X													
Screening criteria	X													
Randomization form		X												
PFT (FVC, FEV1, DLCO)	X			X			X						X	**
HRCT chest (if done as SOC) *	X							X					X	**
HRCT ILD Assessment Form (if done as SOC)	X							X					X	
Dyspnea questionnaire		X		X			X			X			X	X
Patient Global Assessment		X		X			X			X			X	X
HAQ		X		X			X			X			X	X
MMT-8		X		X			X			X			X	X

MDAAT		X		X		X		X				X	X
Physician Global Assessment		X		X		X		X				X	X
Physician Assessment of Change				X		X		X				X	X
Patient Assessment of Change				X		X		X				X	X
SF 36 QoL Questionnaire		X		X		X		X				X	
Brief Evaluation (history/physical)	X			X		X		X				X	X
Six Minute Walk Distance (6MWD)		X		X		X		X				X	
Average daily step count on Fitbit One ® (measured for 7 days at baseline and every month for 6 months)		X		X		X							
Adverse Event/Tolerability Monitoring		X		X		X		X				X	X
Follow Up Call (assess AE's.confirm steroid taper per protocol and subjective clinical worsening)			X	X		X	X	X	X			X	
Bio-specimen Repository Collection		X		X		X		X				X	
RESEARCH SPECIMEN COLLECTION													
PAXGene tube (ml)		8		8		8		8				8	
Stored cells (ml) Green Top		16		16		16		16				16	
Stored Serum (ml) SST		16		16		16		16				16	

* An HRCT scan done as SOC within the last 6 months is required for entry into the trial to meet eligibility criteria.

** HRCT and PFT done as SOC for worsening condition as deemed necessary by investigator.

APPENDIX C: Rescue Medication for ILD Worsening
